### 6.5.2 PROHIBITED MEDICATIONS OR PROCEDURES

Prohibited medications/therapy are listed below in [Table 4](#). The use of a prohibited medication/therapy (unless conditions for use of rescue medications have been met, see [Section 6.6](#)) is a protocol violation and must be recorded in the eCRF. Subjects who receive prohibited rescue treatment will be discontinued from the study and should return for a final ET visit 12 weeks after their last dose. Study procedures at the ET visit should be completed according to the SoA in [Section 1.3](#). In the case of ongoing AEs/SAEs, the subject should be followed up until it has resolved to a stable outcome or subject is lost to follow-up. The date and time of rescue medication administration, as well as the name and dosage regimen of the rescue medication, must be recorded into the eCRF/study database by study site personnel.

All treatments likely to have efficacy in HS need to be discontinued prior to treatment initiation (prior to Day 1) according to [Table 4](#). All medications listed below are also restricted during the study period. If treatment with any of these prohibited treatments is essential, then the subject must notify the study team.

Rescue therapy should be captured in the source documentation and on the appropriate eCRF.

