## 6.6 RESCUE TREATMENT

In the event that an intolerable painful lesion occurs that requires an immediate intervention, at Week 8 or later, physicians will have the option to perform protocol-allowed interventions. Only

two types of interventions are allowed: injection with intralesional triamcinolone acetonide suspension (at a concentration of up to 5 mg/mL, up to 1 cc) and incision and drainage. If incision and drainage is performed, the required over-the-counter antiseptic wash should continue to be used. New systemic and topical therapies following incision and drainage (including antibiotics) are prohibited. Concomitant use of wound care dressings is allowed; however, options are limited to alginates, hydrocolloids, and hydrogels. If a subject requires more than 2 lesion interventions during each of the double-blind phases of the study, they must be discontinued from the study.

All study visit evaluations must occur before any interventions are performed. Any lesion that undergoes an intervention will be documented in the source. The study site will be required to count any lesion that undergoes an intervention as permanently present from the date of the intervention and must account for it in the source and on the appropriate eCRF. All interventions (including local anesthetics) should be recorded in the eCRF for tracking purposes.

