## 5. ANALYSIS SETS

### 5.1 Intent-to-Treat Analysis Set

The Intent-to-Treat (ITT) analysis set will include all randomized subjects. In this analysis set, treatment will be assigned based upon the treatment arm to which subjects were randomized regardless of which treatment they receive. ITT analysis set will be used for primary, secondary, and exploratory efficacy analyses.

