This endpoint measures a 3-point decrease in average HS Pain NRS at a given time point compared to baseline. For each treatment group, the number of subjects with at least a 3-point decrease in average HS Pain NRS will be calculated at each visit. The proportion of such subjects will be calculated for each treatment group at each visit as:

*# of subjects in treatment group with at least 3 point decrease from baseline in average HS Pain NRS at Week x*

---

*# of subjects in treatment group with baseline average HS Pain NRS score  $\geq 3$*

- **Proportion of subjects requiring rescue medication or treatment at each visit**

For each treatment group, the number of subjects receiving rescue medication or treatment (as defined in **Section 6.1.3**) will be calculated at each visit. The proportion of such subjects will be calculated for each treatment group at each visit as:

---

*# of subjects in treatment group requiring rescue medication or treatment by Week x*

---

*# of subjects in treatment group at Week x*

- **Change from baseline in DLQI scores at each visit**

The Dermatology Life Quality Index (DLQI) questionnaire is a simple 10-question validated questionnaire ([Finlay, 1994](#)). These will be assessed at the visits specified in the Schedule of Activities in **Section 3.6.**. Each item is assigned a value from 0 = not at all to 3 = very much and the score is the sum of the individual items (range from 0 to 30). Additional scoring details are below (Cardiff University School of Medicine, 2021):

- If one question is unanswered, this score is allocated to 0.
- If two or more questions are left unanswered the questionnaire is not scored.
- For question 7:
  - an answer of “Yes” is scored as 3;
  - an answer of “Not Relevant” is scored as 0;
  - an answer of “No” is scored depending on the follow up question: *If “No”, over the last week how much has your skin been a problem at work or studying?* “A Lot” is scored as 2 and “A Little” is scored as 1.

Change from baseline in DLQI at each visit will be calculated as the difference between the DLQI at Week x minus the corresponding baseline value.

- **Change from Baseline in IHS4 score at each visit**

The International Hidradenitis Suppurativa Severity Score System (IHS4) is a composite of the number of nodules, abscesses, and draining tunnels. The IHS4 score is calculated at each visit as:

$$(\# \text{ of nodules at Week x}) + 2 * (\# \text{ of abscesses}) + 4 * (\# \text{ of draining tunnels})$$

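### The exploratory rescue proportion in SAP 6.2.4 mixes a cumulative numerator with a visit-specific denominator, and its title describes a third quantity

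*SAP*

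**What the plan says.** SAP 6.2.4 lists the endpoint as "Proportion of subjects requiring rescue medication or treatment at each visit", and the sentence above the formula also speaks of each visit. The formula then has the numerator "of subjects in treatment group requiring rescue medication or treatment by Week x" and the denominator "of subjects in treatment group at Week x". The SAP does not define who is in the group at a given week.

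SAP 5.1 defines the ITT set as all randomized subjects and states that the "ITT analysis set will be used for primary, secondary, and exploratory efficacy analyses". SAP 7.5 makes the Extension Analysis Set the main set for efficacy in the extension period.

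The protocol ties rescue to leaving the study in two places. Section 6.6 covers a subject who "requires more than 2 lesion interventions during each of the double-blind phases of the study, they must be discontinued from the study". Section 6.5.2 states: "Subjects who receive prohibited rescue treatment will be discontinued from the study".

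SAP Section 8, which lists departures from the protocol, does not mention this endpoint.

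**The concern.** The formula says *by* in the numerator and *at* in the denominator. A subject rescued at Week 8 who leaves at Week 10 counts in the Week 16 numerator but, on the natural reading, not in the Week 16 denominator. The numerator is then no longer a subset of the denominator, and the ratio is not a proportion of any defined group of subjects.

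This pairing is peculiar to the rescue endpoint. Most neighbouring formulas in SAP 6.2.4 refer to the same visit in both parts, and the pain responder formulas use a fixed baseline denominator. Because the title and the formula also disagree on whether the measure is cumulative or per visit, two programmers could produce different tables in good faith.

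Rescue is the intercurrent event named in the primary estimand (Protocol 9.4.5, SAP 7.5.1), and data after it are treated as missing. A reader judging how far rescue differs between arms would look at this endpoint. An artefact of dropout in it could be mistaken for a difference in rescue.

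**Working it through.** **Inputs from the documents.** N = 40 randomized per arm and 10% dropout before Week 16 (Protocol 9.2, SAP 3.5). The plan's own attrition figure reproduces: 40 × (1 − 0.10) = 36 per arm, so d = 4 have left.

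**Assumed inputs.** The documents give no rescue rate and no attrition after Week 16. I take r = 4, 8 or 12 subjects ever rescued of 40.

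**Step 1: formula as written against cumulative rescue in the randomized arm.** The first is r/(N − d), the second r/N. Their ratio is N/(N − d) = 40/36 = 1.11, whatever r is.

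| r (assumed) | r/40 | r/36 as written |
|---|---|---|
| 4 | 10.0% | 11.1% |
| 8 | 20.0% | 22.2% |
| 12 | 30.0% | 33.3% |

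**Step 2: formula as written against ever-rescued among subjects still on study.** Let k of the 4 leavers be rescued subjects, with r = 8. The on-study proportion is (8 − k)/36.

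| k | On-study proportion | As written |
|---|---|---|
| 0 | 8/36 = 22.2% | 22.2% |
| 2 | 6/36 = 16.7% | 22.2% |
| 4 | 4/36 = 11.1% | 22.2% |

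The formula agrees with the cumulative ITT proportion only if nobody has left. It agrees with the on-study proportion only if no rescued subject has left. It is also not rescue since the previous visit, which is what the title suggests, because the numerator carries forward all earlier rescue.

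**Step 3: unequal dropout.** Suppose 8 of 40 are rescued in each of two arms, with 2 leavers in one and 6 in the other (assumed; the average is the planned 4). The reported values are 8/38 = 21.1% and 8/34 = 23.5%. The gap of about 2.5 points comes from dropout alone.

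**Step 4: later visits.** If 8 of 40 had left, the factor would be 40/32 = 1.25 (8 rescued shown as 25.0%). If 12 had left, it would be 40/28 = 1.43 (28.6%). Both losses are assumptions.

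**The case against.** The strongest reply is that the denominator is undefined rather than wrong. Many neighbouring formulas restrict explicitly to subjects with a score or data at the visit, and this one does not. With SAP 5.1 in mind, the group at Week x could mean every subject assigned to the arm, and then there is no inflation. Protocol 9.4.6.1, which Protocol 9.4.7 extends to exploratory endpoints, keeps subjects with missing scores as not meeting the criterion, and that also points to a full denominator. This reading is possible, but it leaves the words tying the denominator to Week x without any function, and the SAP nowhere states it. The conflict between title and formula remains on either reading.

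The link from rescue to departure is also partial. Protocol 6.6 removes a subject only after more than two interventions in a phase, so those with one or two may stay. It opens protocol-allowed rescue "at Week 8 or later, physicians will have the option to perform protocol-allowed interventions", so within the placebo-controlled period mainly Weeks 8, 12 and 16 are exposed. This limits the size of the effect without removing it.

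The comparison value r/N is not simply the true rescue rate either. It counts an unrescued leaver as never rescued, so it can understate rescue in an arm with more dropout. That stands, and the definition should say so.

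A reader might infer that the exact confidence intervals and the Cochran-Mantel-Haenszel test for this endpoint are invalid. The documents do not support that. SAP 7.5.3 only summarizes the rescue proportion by frequency and percentage, and its distribution tests are for other scales. Intervals and tests reach rescue only through Protocol 9.4.6.1 and 9.4.7. The SAP's CMH template tabulates stratum by treatment by outcome, with each subject in one cell, so the mismatched ratio affects a displayed percentage and not that test.

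A reader might also infer a large distortion, for instance 8/30 = 26.7% against 20.0%. That needs 10 of 40 subjects to have left, which is 25%, against the 10% planned to Week 16.

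**Conclusion.** The formula is wrong as written and should be corrected, but the consequence is small. On the natural reading of the denominator, it equals neither cumulative rescue in the randomized arm nor a per-visit proportion, and it departs from the ITT set assigned to exploratory efficacy. At planned attrition the cumulative proportion is inflated by a factor of 1.11, or about 1 to 3 percentage points for assumed rescue rates of 10% to 30%. The inflation is larger if more subjects leave and unequal across arms if dropout is unequal.

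These sizes rest on assumed rescue counts, on the planned 10% dropout, and on reading the denominator as subjects still on study. Any departure shrinks the denominator; only the departure of a rescued subject breaks the subset relation. If all leavers were unrescued, the ratio would be a valid on-study proportion, though still not cumulative rescue in ITT.

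This is one exploratory endpoint. The primary analysis does not use it, and SAP 7.4.3 separately summarizes rescue use on the Safety Analysis Set and lists rescue medications.

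**What to change.** Choose one definition and make the title, the lead-in sentence and the formula agree with it.

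- **Cumulative.** Through Week 16: subjects with any rescue by Week x over all ITT subjects in the arm. After Week 16: subjects with any rescue since the Day 113 dose over the Extension Analysis Set, by extension regimen. State that subjects who leave unrescued count as not rescued. One ITT denominator cannot serve Weeks 20 to 40, because placebo subjects are re-randomized at Day 113 and those who left earlier belong to no extension regimen.
- **Per visit.** Subjects with rescue since the previous visit over subjects on study at the start of that interval.

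The change is one revised definition, with a separate denominator for the extension if the cumulative form is chosen. No new data are needed: Protocol 6.5.2 and 6.6 already require rescue medication dates and all interventions to be recorded, and SAP 6.1.3 names the case report form pages.

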### 6.3 Pharmacokinetic Variables

Serum concentration time data will be collected following imsidolimab administration to evaluate the PK profile of imsidolimab. Samples from subjects who received imsidolimab only will be analyzed for PK; no placebo samples will be analyzed. Pharmacokinetic samples will be collected at the time points indicated in **Table 3** below.

**Table 3 Pharmacokinetic Sample Collection and Time Points**

Study Visit	Pharmacokinetic Sample Time Point (Serum)
Day 1	Pre-dose 2 hr. ( $\pm$ 10 min) post-dose
Day 29	Pre-dose
Day 57	Pre-dose
Day 85	Pre-dose
Day 113	Pre-dose
Day 141	Pre-dose
Day 169	Pre-dose
Day 197	Pre-dose
Day 225	Anytime
Day 253	Anytime
Day 281	Anytime

Abbreviations: hrs., hours; min, minutes; PK, pharmacokinetic.

Non-compartmental analysis (NCA) will not be conducted due to minimal PK sampling. However, other presentations of PK information may be added at the discretion of the PK scientist.

Population PK modeling may be performed by the Sponsor or another designated sponsor, and if done, will be described in a separate PK analysis plan and report.

#### 6.4 Immunogenicity Variables

- **Presence of ADA to imsidolimab**

ADA to imsidolimab will be collected at the time points indicated in **Table 4** below:

**Table 4 ADA Sample Collection and Time Points**

Study Visit	ADA Sample Time Point
Day 1	Pre-dose
Day 29	Pre-dose
Day 57	Pre-dose
Day 85	Pre-dose
Day 113	Pre-dose
Day 141	Pre-dose
Day 225	Anytime
Day 281	Anytime

Abbreviations: ADA, Anti-drug antibodies.

ADA assessments will be conducted utilizing a tiered approach that includes:

1. A screening assay that identifies potential binding ADA in serum samples.
2. A confirmatory assay that confirms the binding specificity of the drug.
3. A titer assay that measures the titer of confirmed ADA. A sample that has been found negative in the screening or confirmatory assay will not have a titer value.

A subject will be considered to be positive for imidolimab-induced immunogenicity if the subject has one confirmed positive ADA response after dosing. Confirmed positive ADA samples may also be tested for neutralizing ADA.

Antidrug antibody variables include status (positive or negative) and titers as follows:

- Total subjects with negative ADA response at all times
- Total subjects with confirmed positive ADA response at any time
- Pre-existing immune-reactivity, defined as either
  - A positive ADA at baseline with all post-treatment ADA results negative, or
  - A positive ADA at baseline with all post-treatment ADA responses less than 4-fold over baseline titer levels.
- Treatment-emergent: any post-treatment positive ADA when the baseline ADA result is negative
- Treatment-boosted: any post-treatment positive ADA that is greater than or equal to 4-fold over baseline titer level when baseline is ADA positive
- Overall ADA incidence: the proportion (%) of subjects with positive ADA, either treatment-induced or treatment-boosted, relative to all imidolimab treated subjects
- Titer values

## 6.5 Biomarker Variables

- **Biomarkers analysis including, but not limited to interleukin (IL)-1, IL-36, Th-17 cytokines such as IL-17A, and markers of neutrophils and dendritic cells infiltration**

Tape strips and optional noninvasive collection of drainage fluid will be collected at the visits specified in the Schedule of Activities in **Section 3.6** to measure cutaneous biomarkers including, but not limited to, IL-36 receptor (IL-36R), Th-17 cytokines such as IL-17A, and markers of neutrophils and dendritic cells infiltration. The analysis of tape strips biomarkers may be performed by an additional third party designated by the Sponsor.

## 6.6 Safety

Adverse events, serious adverse events (SAEs), AEs leading to discontinuation of study treatment, and AEs leading to withdrawal from study, as well as changes in vital signs, clinical laboratory parameters (hematology, biochemistry, and urinalysis), and 12-lead ECGs will be evaluated to meet the safety objectives of the study.

### 6.6.1 Study Day and Visit Window Definitions

Adverse Events will be closely monitored on each patient throughout their participation in the study. Adverse Events will be reported by the study period that they occurred in as detailed in the Data Handling Rules Appendix. Safety assessments for other safety variables will occur as detailed in the Schedule of Activities in **Section 3.6**. Safety data assessed per the Schedule of Activities will be allocated according to the rules for efficacy data in **Section 6.2.1**.

### 6.6.2 Extent of Exposure to Study Medication and Compliance

The number of doses received by the patient for a study treatment will be calculated as the sum of the doses received in the placebo-controlled period, extension period, and overall.

The number of days of exposure to a study treatment will be defined as Date of last treatment – Date of first dose of treatment + 1.

Total dose received will be the total amount (in mg) of study treatment taken during the entire treatment period (placebo-controlled + extension).

Dose intensity for a specific period is defined as (cumulative total dose received during a period/cumulative total expected per-protocol dose during the same period) x 100%. Dose intensity will be summarized by treatment group and summarized separately for placebo-controlled period, extension period, and overall.

### 6.6.3 Adverse Events

AEs experienced by the subjects will be collected throughout the entire study and will be coded using the latest version of the MedDRA specified in the approved Data Management Plan. Analysis of adverse events will be carried out on the Safety Analysis Set during the placebo controlled period and the Extension Analysis Set for the extension period.

An adverse event is considered treatment-emergent if the date of onset is during or after first dose of study treatment, or if the AE present at baseline that worsens in either intensity or frequency after first dose of study treatment. An adverse event that begins on the same date as the first dose of study treatment is treatment-emergent if the AE begins on or after the time of first dose or if the time of AE onset is unknown.

The severity of AEs will be evaluated as “Mild”, “Moderate”, and “Severe” using the criteria specified in [Section 8.2.1.3.1](#) of the study protocol.

AEs will be classified as related, possibly related, unlikely to be related, or unrelated to study treatment using the criteria specified in [Section 8.2.1.3.2](#) of the study protocol.

Adverse events will be categorized as serious or non-serious using the definition specified in [Section 8.2.1.2](#) of the study protocol.

#### Events with Partial Onset Dates

All treatment-emergent adverse events (TEAEs) will be included in the tabulations regardless of the completeness of the onset dates. Partial dates will be imputed in order to determine if an AE is treatment-emergent using the imputation rules in [Appendix 1](#); however, imputed dates will not be provided in the data listings.

**Uncoded Events:** Before the database lock, uncoded events will be assigned the string “UNCODED” as the body system, and the verbatim term will be used as the preferred term, so they can be included in the summary tables. In the final dataset, all the adverse events will have been coded.

#### 6.6.3.1 Deaths

All deaths which occur during the study will be listed.

#### 6.6.4 Laboratory Data

Clinical laboratory tests that will be performed in this study are summarized in [Appendix 10](#) of the study protocol. Local laboratory samples will be collected in the electronic case report form (eCRF) when the central laboratory results are not available immediately, and the Investigator needs to take an immediate decision for any safety concerns. All lab data will be listed, but only hematology, biochemistry, and urinalysis will be summarized.

#### Conversion to the International System of Units

All laboratory data will be stored in the database with the units in which they are originally reported. Laboratory data in summary tables and patient data listings will be presented in the International System of Units (SI units). Laboratory data not reported in SI units will be converted to SI units before further processing or data analysis.

#### Abnormal Values

Based upon laboratory normal ranges, laboratory test results will be categorized according to the normal range as low, normal, and high. Subjects with laboratory data outside the normal range will be listed with abnormal values flagged.

## 6.6.5 Vital Signs

Vital signs including body temperature (°C), pulse rate (bpm), systolic and diastolic blood pressure (mmHg), respiratory rate (breath/min), weight (kg), and height will be obtained in accordance with the Schedule of Activities in **Section 3.6**. Changes from baseline in vital signs variables will be evaluated.

If there are multiple vital sign values for the same parameter at a given visit, the last value will be chosen for analysis.

## 6.6.6 Electrocardiogram (ECG)

Changes from baseline in heart rate, as well as RR, PR, QRS, QT, and corrected QT interval by Fredericia (QTcF) intervals will be collected according to the Schedule of Activities in **Section 3.6**. Changes in ECG parameters between baseline and each subsequent scheduled assessment will be calculated.

The outcome of the overall evaluation is to be recorded as normal/abnormal in the eCRF, with any abnormalities being recorded as not clinically significant or clinically significant.

## 6.6.7 Other Safety Assessments

The following assessments will be performed, but will not be used to define additional safety parameters for the study: chest X-ray, physical examination, tuberculosis (TB) screening, pregnancy tests (serum or urine), viral serology, and follicle-stimulating hormone (FSH). Data from these assessments will be captured in the eCRF and will be listed.

# 7. STATISTICAL ANALYSIS

## 7.1 Data Handling Rules and Definitions, Including Handling of Missing Data

Except where specified, all continuous variables will be summarized with descriptive statistics (the number of non-missing values, mean, standard deviation, first and third quartiles, median, minimum, and maximum). Where data have been logarithmically transformed for analysis, the summary statistics on the back-transformed data will include the geometric mean (calculated as  $\exp(m)$ ), where  $m$  is the mean of the data on the log scale) and the coefficient of variation (calculated as  $100\sqrt{[\exp(s^2)-1]}$ , where  $s$  is the standard deviation of the data on the log scale). All categorical variables will be summarized with frequency counts and percentages. Tabulations will be provided based on all subjects combined, as well as separately by treatment group.

Missing data will be maintained as missing in the analysis datasets, unless specified otherwise. For variables where missing data are imputed, the analysis dataset will contain a new variable with the imputed value and the original variable value will be maintained as missing.

